3.4.4 Vital Signs

Vital signs, including systolic and diastolic blood pressure and heart rate, will be measured at timepoints specified in Table 2 Schedule of Procedures in the protocol.

Vital signs will be summarized descriptively, including the change and percent change from baseline at each visit by treatment group and overall. Number and percentage of patients with any clinically significant change from baseline will be summarized at each visit by treatment group.

3.4.5 Electrocardiograms

A standard 12-lead ECG will be performed at timepoints specified in Table 2 Schedule of Procedures in the protocol. Continuous ECG parameters will be summarized with descriptive statistics by treatment group for each visit. The number and percentage of patients with clinically significant changes will be tabulated by treatment group. In addition, a summary of QTcF measurements will be summarized by treatment group for the following predefined criterion:

- QTcF > 450 for male

- QTcF>470 for female.

QTcF will be calculated according to the following formula:

$$QTcF = \frac{QT}{\sqrt[3]{RR/1000}}$$

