4.3 Withdrawal Criteria

A patient may prematurely discontinue study drug and/or withdraw from the study at any time. A distinction must be made between premature discontinuation of study drug and withdrawal from the study. A patient may prematurely discontinue study drug and still continue his/her participation in the study.

The reasons for premature discontinuation of study drug and for withdrawal from the study must be documented in the eCRF. Reasons for premature discontinuation of study drug include, but are not limited to, the following:

- Withdrawal of consent/assent;
- Any event, laboratory abnormality, intercurrent illness, or other medical condition that indicates to the Investigator that continued participation is not in the best interest of the patient;
- Pregnancy;
- Patient failure to comply with Protocol requirements or study-related procedures;
- Termination of the study by the Sponsor or regulatory authority;

- Initiation of medications known to be potent CYP3A4 inhibitors (itraconazole, lopinavir/ritonavir, telaprevir, clarithromycin, ritonavir, ketoconazole, indinavir/ritonavir, conivaptan, and voriconazole), potent CYP3A4 inducers (avasimibe, carbamazepine, enzalutamide, mitotane, nevirapine, phenobarbital, phenytoin, rifabutin, rifampicin, rifapentine, and St John's wort), or potent UGT1A9 inhibitors and inducers (mefenamic acid and rifampicin);
- The patient experiences mean QT prolongation (mean QTcF interval >500 milliseconds AND increase by >60 milliseconds over the mean baseline QTcF);
- Severe allergic reactions to the study drug;
- The patient has CTCAE Grade ≥ 2 anemia AND the retest absolute reticulocyte count is below 50% of the baseline value. In this case, study drug will not be resumed and will be permanently discontinued; or
- The patient has suspected DILI meeting [Criterion 3](#) in [Appendix C](#).

Unless a patient withdraws his/her consent/assent to participate in the study, all patients should be encouraged to complete the remaining study visits, regardless of whether they are still receiving study drug.

For patients who are withdrawn from the study prior to completion of Study Visit 8, the Early Termination Visit procedures will be completed, if possible, at the time the decision is made to withdraw the patient. The Early Termination Visit will consist of all of the Study Visit 8 procedures. The reason for patient withdrawal must be documented in the eCRF.

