8.10 Electrocardiograms

12-lead ECGs will be collected at timepoints specified in [Appendix A](#), including at Screening, Day 1 (pre-dose and 3 and 6 hours post-dose), Weeks 2, 6, 12, and 18 (pre-dose), Week 24 (pre-dose and 3 and 6 hours post-dose), and at the Follow-up Visit. Timing windows for ECGs are ± 10 minutes for 3 hours post-dose and ± 20 minutes for 6 hours post-dose.

ECGs should be collected in triplicate, 1 to 3 minutes apart, and read locally. Investigators and site staff are encouraged to consult with a local cardiologist, if needed, to interpret suspected QT prolongation or other clinically significant abnormalities.

If collected at the same time point as PK blood draws, ECGs should be recorded before blood draws to avoid effects of blood draw on autonomic tone.

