9.2.1 Analysis of Safety

To assess the primary objective, the primary safety estimand for SAE is defined by the following key attributes, according to the framework provided in International Council for Harmonisation (ICH) E9 (R1):

Treatment: Setanaxib treated patients compared to placebo.

Population: The SAS comprised of all randomized patients who took at least 1 dose of the study drug.

Variable of interest: SAEs.

Intercurrent event handling: All events will be counted regardless of early discontinuation of treatment, up to 30 days post-last dose of study drug.

Summary measure: Count and percentage of patients experiencing SAEs during the Treatment Period up to 30 days post-final dose.

The analysis of the primary endpoint will be performed using the SAS. The number and percentages of patients with SAEs and treatment-emergent AESIs will be presented by treatment group, system organ class, and preferred term. Additional summaries of AEs, TEAEs, AEs leading to discontinuation of study treatment, and AEs by severity, seriousness, and relationship to study drug(s) will be presented.

Clinical laboratory parameters, vital signs, ECGs, thyroid, hearing and physical examinations will be summarized by treatment group by visit. Change from baseline values by visit will be presented for the continuous parameters. The count (and percentage) of patients with clinically significant changes will be tabulated by treatment group.

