3.1.3 Definition of Baseline

Baseline is defined as the last measurement prior to the first dose of study drug, unless otherwise stated.

Liver tests (Alanine aminotransferase, Aspartate aminotransferase, and total bilirubin) baseline values are determined by averaging the values obtained at screening visits 1 and 2 to obtain the arithmetic mean.

UPCR and eGFR baseline values are defined as the geometric mean of 2 assessments prior to randomization.

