3.4.3 Clinical Laboratory Tests

Clinical laboratory evaluations (including serum chemistry, hematology, endocrinology/thyroid function, and urinalysis) will be obtained as indicated in Table 2 Schedule of Procedures in the protocol and processed by a central laboratory. A list of laboratory tests to be performed are included in Appendix B in the protocol.

Laboratory values and changes from baseline will be presented at each visit and baseline by laboratory test. In addition, the number and percentage of patients with parameters outside the normal range (below the lower limit of normal ($<LLN$) or above the upper limit of normal ($>ULN$)) will be presented by visit and treatment group. The count and percentage of patients with clinically significant changes will be tabulated by treatment group. Clinically significant changes will be identified as any TEAEs related to significant change in laboratory test. Medical review of AE will be performed by Medpace to identify any clinically significant changes. The provided classifications will be used in analysis.

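### The SAP's ECG section omits, undeclared, the change from baseline the protocol promises; its QTcF categories repeat the entry limits, and no rule combines triplicate ECGs

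*SAP*

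**What the plan says.** Protocol 9.2.1 sets the scope, "Clinical laboratory parameters, vital signs, ECGs, thyroid, hearing and physical examinations will be summarized by treatment group by visit", and then commits to a second summary: "Change from baseline values by visit will be presented for the continuous parameters". ECG intervals are continuous, so they are covered.

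SAP 3.4.5 plans three things for ECGs:
- "Continuous ECG parameters will be summarized with descriptive statistics by treatment group for each visit";
- by arm, how many patients had ECG changes of clinical significance, as counts and percentages;
- a summary of QTcF above 450 (male) and above 470 (female).

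The neighbouring SAP sections go further. For laboratory tests (3.4.3): "Laboratory values and changes from baseline will be presented at each visit and baseline by laboratory test". Section 3.4.4 gives change and percent change for vital signs. SAP 6 lists two changes from the protocol, one on treatment-emergent SAEs and one on an MMRM for eGFR. Neither concerns ECGs.

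On baseline, SAP 3.1.3 states: "Baseline is defined as the last measurement prior to the first dose of study drug, unless otherwise stated". It makes exceptions for liver tests, UPCR and eGFR, but not for ECGs. Protocol 8.10 states: "ECGs should be collected in triplicate, 1 to 3 minutes apart, and read locally". Readings are pre-dose, 3 h and 6 h on Day 1 and at Week 24, and pre-dose at Weeks 2, 6, 12 and 18. The protocol's on-treatment QTcF criterion (4.3, also 1.6.2) joins a mean QTcF above 500 ms to an "increase by >60 milliseconds over the mean baseline QTcF".

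**The concern.** ECG change is a named safety endpoint. The dog studies showed transient QTc prolongation at 100 mg/kg/day and above (Protocol 1.3.2), and Protocol 5.3 expects adult exposure similar to the NOAEL. With about 18 patients and no formal testing, the descriptive tables are the planned by-arm evidence on QTcF.

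Patients differ in QTcF before treatment, and in a small trial that spread dominates a comparison of raw visit values. Change from baseline removes most of it, provided QTcF varies less within patients than between them. Tables built from SAP 3.4.5 as written would also lack any count that matches the limits the protocol applies to individual patients. A programmer would have to decide how several tracings at one time point become one value.

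**Working it through.** The documents give no ECG effect size, SD or power, so there is no figure of the plan to reproduce. Steps 1 to 3 use the documents alone. Steps 4 and 5 are illustrations on assumed values.

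**1. Change from baseline, side by side**

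| Parameter | Protocol 9.2.1 | SAP |
|---|---|---|
| Laboratory | change by visit | change stated (3.4.3) |
| Vital signs | change by visit | change and percent change stated (3.4.4) |
| ECG | change by visit | not mentioned (3.4.5), not declared (6) |

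**2. QTcF categories**

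The SAP limits equal those of exclusion criterion 11 (Protocol 4.2). A rise of 60 ms just reaches the limit from 450 − 60 = 390 ms (male) or 470 − 60 = 410 ms (female). From any lower baseline, a rise above 60 ms can stay within the limit. For example, a male going from 385 to 447 ms rises 62 ms and is not flagged, while a male going from 448 to 453 ms rises 5 ms and is. A patient above 500 ms falls in the 450/470 row but cannot be told apart there from one at 453 ms.

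**3. Replicates**

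On Day 1 and at Week 24 there are 3 time points × 3 tracings = 9 tracings. The SAP does not say how they become one value per time point. Vital signs are also taken three times, but Protocol 8.9 supplies a rule (the lowest value is recorded). ECGs have no such rule.

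**4. Precision with and without change from baseline (assumed SDs)**

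Let b, o and r be the between-patient, between-occasion and replicate SDs, with 12 and 6 patients (2:1 of 18) and triplicates averaged.
- SD of a visit value = √(b² + o² + r²/3)
- SD of a change = √(2(o² + r²/3))
- 95% half-width for the arm difference = t(16) × SD × √(1/6 + 1/12) = 2.12 × SD × 0.5 = 1.06 × SD

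| b / o / r (ms) | SD, value | Half-width | SD, change | Half-width | Ratio |
|---|---|---|---|---|---|
| 12 / 5 / 4 | 13.2 | 14.0 | 7.8 | 8.3 | 0.59 |
| 15 / 6 / 5 | 16.4 | 17.4 | 9.4 | 10.0 | 0.57 |
| 20 / 8 / 7 | 21.9 | 23.2 | 12.7 | 13.4 | 0.58 |

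The interval narrows by 41% to 43%. The gain exists whenever o² + r²/3 is below b². In the first row that is 25 + 5.3 = 30.3 against 144.

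If one tracing were used at baseline and a triplicate mean on treatment, the half-widths for change would be 9.0, 10.9 and 14.7 ms. Against 8.3, 10.0 and 13.4 ms, that is 8% to 10% wider.

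**5. What the 450/470 rows show of a moderate shift (assumed values)**

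The assumptions are mean baseline 400–420 ms (male) or 410–430 ms (female), between-patient SD 15–20 ms, within-patient SD 6–8 ms, and baseline at or below the limit. After a uniform 10 ms rise, the simulated chance p that a patient exceeds the limit at a given visit is 0.0059 to 0.1153 (male) or 0.0010 to 0.0577 (female). The chance that none of 12 treated patients does, (1 − p)^12, is 0.93 to 0.23 if all are male and 0.99 to 0.49 if all are female.

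**The case against.** The strongest reply is that the commitment was never withdrawn. SAP 3.1.4 defines change from baseline generally, and section 6 does not list ECG change as removed, so this looks like a drafting slip. It probably is one. But 3.1.4 says how change is calculated, not which parameters get it. Silence in section 6 is also weak evidence that a protocol commitment stands. The move from a chi-square test (Protocol 9.2.2) to Fisher's exact test (SAP 3.5.1) is not listed there either.

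A reader might infer that a QTcF effect would go unseen. The documents do not support that:
- Values by arm and visit are summarised with mean, median, SD, minimum and maximum (SAP 3.1.5). An arm-level shift in means can be read off when the same patients contribute, and the maximum shows whether anyone passed 500 ms.
- Clinically significant ECG changes are also counted, so the 450/470 rows are not the whole tabulation. However, SAP 3.4.3 says how such changes are identified for laboratory tests, and 3.4.5 does not do so for ECGs.
- A patient meeting both parts of the protocol criterion stops study drug with the reason recorded. ECG abnormalities requiring action on study drug should usually be reported as AEs, and TEAEs leading to discontinuation are tabulated and listed.
- All data are listed by patient, and the IDMC sees unblinded safety data.

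These routes leave out the spread of within-patient change by arm and a count of rises above 60 ms. Such a rise that stays under 450/470 ms does not meet the joint criterion, so the gap is in description, not in detecting patients who meet it.

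A reader might also infer that baseline is a single tracing. SAP 3.1.3 does not say so: a measurement may equally be the triplicate assessment, and Protocol 4.3 refers to a mean. Nor does a replicate-only calculation, √(4/3)/√(2/3) = 1.41, size the problem. It assumes averaging on treatment but not at baseline, ignores between-occasion variation, and concerns a change score the SAP does not specify for ECGs.

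Finally, presenting results by time point can be called table layout. Vital signs have the same wording, and SAP 3.4.5 does refer to the schedule's time points. That is fair, but Tmax is 0.5 to 3 h (Protocol 1.4.1), so time after dose deserves its own rows.

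**Conclusion.** The point holds on three counts, all from the text. The ECG change from baseline promised in Protocol 9.2.1 is absent from SAP 3.4.5 and undeclared. The numeric QTcF categories repeat the entry limits and do not count the >500 ms and >60 ms limits the protocol uses. The SAP states no rule for combining triplicates.

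The first count matters most. Change narrows the interval for the arm difference by a little over 40% under the assumed SDs, provided within-patient variance is below between-patient variance. No such interval is planned, so this measures how informative the summary is and is not a loss of power. The replicate rule matters less, at 8% to 10% of interval width even if one baseline tracing were used. The 390 and 410 ms thresholds need no assumption. The primary endpoints are unaffected. This should be corrected before database lock.

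**What to change.** In SAP 3.4.5:
1. Present QTcF and its change from baseline by treatment group, visit and nominal time point (pre-dose, 3 h and 6 h on Day 1 and at Week 24). Present change from baseline by visit for the other continuous ECG parameters, as Protocol 9.2.1 requires.
2. Use the mean of the triplicate at each time point. Define ECG baseline as a mean, in line with Protocol 4.3, and state which pre-dose readings form it. ECGs are taken at Screening as well as on Day 1, and the protocol does not say which readings count.
3. Beside the 450/470 ms rows, add counts of patients with QTcF above 500 ms, a rise above 60 ms, and both. These are the protocol's existing limits, used here for tabulation. No clinical rule changes.
4. Add a line on how clinically significant ECG changes are identified, as 3.4.3 does for laboratory tests.

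If leaving out the change from baseline was intended, declare it in SAP 6 with the reason. The cost is SAP wording and one extra table. All the tracings are already collected.

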3.4.6 Physical Examinations

A physical examination will be performed at timepoints specific in Table 2 Schedule of Procedures in the protocol.

Physical examination parameters will be recorded as normal, abnormal or not done. Abnormal values will be assessed as clinically significant or not clinically significant. Count and percentages for physical parameters will be summarized by treatment group and in total. The number and percentage of patients with clinically significant changes from baseline will be tabulated by treatment group.

3.4.7 Hearing Examination

A hearing examination will be performed at timepoints specific in Table 2 Schedule of Procedures in the protocol.

Hearing examination, including bone- and air-conduction, will be recorded as no change from baseline, no significant change from baseline or clinically significant change from baseline. All values will be summarized by treatment group and by visit. The number and percentage of patients with clinically significant change from baseline will be tabulated by treatment group.

3.5 Efficacy Assessment

Efficacy data will be summarized using the FAS Population.

3.5.1 Urine Protein to Creatinine Ratio (UPCR)

The ratio of UPCR at 24 weeks compared to baseline will be analyzed using a mixed model repeated measurement (MMRM) approach and incorporate UPCR data from 6 weeks, 12 weeks and 24 weeks. Baseline and 24 weeks UPCR will be calculated as the geometric mean of 2 assessments and log-transformed prior to inclusion in the analysis model. The model will include fixed effects for treatment, visit, and treatment by visit interaction, along with the log-transformed baseline value as a covariate. Patient will be included as a random effect. An unstructured covariance matrix will be used to model the within patient correlation of data. If the model does not converge, other covariance structures may be considered. The Kenward-Roger approximation to estimate the degrees of freedom will be used. Model assumptions will be assessed using residual plots (such as q-q plots, histograms) and, if not met, other data transformations or non-parametric approaches may be considered. The LS mean and 2-sided 95% confidence intervals will be estimated.

The analysis will be implemented using SAS® Proc Mixed. Sample SAS code below:

```
*****
** TRT          = treatment group
** VISIT        = Visit name
** USUBJID      = Patient ID
** CHG_UPCR     = Change of log-UPCR at each visit from baseline
** BASE        = log-baseline UPCR
```

```
*****  
proc mixed data=data;  
  class TRT USUBJID VISIT;  
  model CHG_UPCR = TRT VISIT BASE TRT*VISIT/ddfm=kr;  
  repeated VISIT/ sub = USUBJID type = un;  
  estimate 'Week 24 effect' TRT -1 1;  
  lsmeans TRT*VISIT/cl pdiff;  
run;
```

The proportions of patients achieving a 25% reduction in UPCR at 24 weeks from baseline in the setanaxib group will be compared to placebo group using a Fischer's exact test.

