As an additional safety measure, emerging safety and tolerability data will be regularly reviewed by an unblinded Independent Data Monitoring Committee (IDMC) with the first assessment after 2 patients have had the opportunity to complete at least 12 weeks of study treatment. Ad-hoc IDMC meetings may be scheduled as requested by the Sponsor or the IDMC. If there is a case of suspected DILI, study enrollment will be paused awaiting IDMC review and recommendation.

The results of this first study in Alport syndrome will be used to assess the safety of setanaxib in this patient population, including adolescents, and to aid the design of further Phase 2/3 studies of setanaxib in Alport syndrome.

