5 STUDY TREATMENTS

5.1 Treatment Groups

5.1.1 Setanaxib

Patients will receive the following setanaxib doses according to age at the time of consent/assent:

- For patients aged 12 to 17 years: 1200 mg/day (800 mg morning + 400 mg evening) for 24 weeks; and
- For patients aged ≥ 18 years: 1600 mg/day (800 mg BID) for 24 weeks.

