The relationship between dose and inhibition of NOX1 and NOX4 pathways in humans is not clearly established, but estimates based on preclinical in vitro experiments and human PK suggest that at a dose of setanaxib of 800 mg BID, the average target inhibition over the dosing interval is about 80%. This is superior to the 400 mg BID dose level (about 68% inhibition). These estimates suggest that the 800 mg BID dosing regimen may provide sufficient target inhibition to evaluate the mechanism of action and clinical effects of setanaxib.

The dose selection for the adolescent patients is based on results from completed and ongoing studies, indicating that a dose of setanaxib of 800 mg BID in adults is safe, well tolerated, and may provide clinical benefit in adult patients. Since there is no suggestion that the pharmacology^{29,30,31,32} or safety and tolerability of setanaxib will be different in adolescent patients with Alport syndrome, the dose selection for adolescent patients aims to achieve the same systemic exposure levels as those seen in adults following dosing at the 800 mg BID dose level.

Available data for setanaxib suggest a drug disposition profile where renal clearance of unchanged parent drug represents a negligible portion of the elimination and where metabolism via UGT1A9-mediated glucuronidation and CYP3A4 are the dominant elimination pathways, with only minor contributions from other elimination pathways.

Following allometric principles, a dose level of 1200 mg/day (800 mg morning + 400 mg evening) for the 12 to 17 years of age range (restricted to a body weight of at least 40 kg) has been selected. On average, a 40 kg patient at 1200 mg/day is expected to have approximately 14% higher exposure (AUC) than a 70 kg patient at 1600 mg/day.

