7.3 Estimated Glomerular Filtration Rate

Plasma samples for eGFR will be collected at timepoints specified in Appendix A.

The central laboratory will calculate the eGFR using the CKD-EPI formula for patients ≥ 18 years of age and the revised bedside Schwartz formula for patients 12 to 17 years of age.

Note: Two eGFR samples will be collected at Week 24, at least 1 week apart but no more than 2 weeks apart, with the last sample collected during the Week 24 study visit.

eGFR history up to 12 months prior to signing informed consent/assent, including local laboratory results, will be collected.

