2.2 Study Design

2.2.1 Overview

This is a randomized, double-blind, placebo-controlled Phase 2a study assessing oral setanaxib in patients with Alport syndrome. The safety, tolerability, pharmacokinetics (PK), pharmacodynamics (PD), and preliminary efficacy of setanaxib will be assessed over 24 weeks of treatment. Patients are required to have persistent proteinuria (UPCR ≥ 90 mg/mmol [0.8 g/g]) despite treatment with a stable dose of RAS (Renin-angiotensin system) inhibitor therapy (ACEis and/or ARBs) at the maximum allowed dose or maximum-tolerated daily dose for at least 8 weeks prior to consent/assent. Patients should remain on their regimens of RAS inhibitors for the whole duration of the study.

This study aims to assess the safety of setanaxib as an add-on treatment to current RAS inhibitor treatment, in patients with Alport syndrome at risk of disease progression and with limited treatment options available. The double-blind, placebo-controlled design is chosen to provide safety data and preliminary efficacy for setanaxib in addition to the standard of care treatment in this patient population with a standard of care (with placebo) arm as reference. This will help to guide the design of further Phase 2/3 studies of setanaxib in Alport syndrome.

The study is planned to enroll and treat approximately 18 patients, eligible patients will be randomized in a 2:1 ratio, respectively to the following treatment groups:

- Setanaxib group:
 - For patients aged 12 to 17 years: 1200 mg/day (800mg morning + 400mg evening) for 24 weeks.
 - For patients aged ≥ 18 years: 1600mg/day (800mg twice daily) for 24 weeks.
- Placebo group: matching placebo tablets daily.

Up to 6 patients should be in the age group of 12 to 17 years old at the time of consent/assent, and a minimum of 12 patients should be ≥ 18 years of age. To ensure balance among treatment groups, randomization will be stratified by age group (12 to 17 year of age and ≥ 18 years of age) at the time of consent/assent.

Patients must take the first dose of study drug in the presence of site staff during Study Visit 3 (Day 1). Similarly, the morning dose at the week 2, week 12, and week 24 visit should be taken at the study site, to allow for proper PK sampling.

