In the analysis phase, the ratio of eGFR at 24 weeks compared to baseline will be calculated for each patient within each imputed dataset. The ratio of eGFR of the log-transformed data will be analysed using Robust Regression with independent variables of treatment and log-transformed baseline eGFR. M-estimation will be used with Huber weights. Sample SAS code below:

```
*****
** TRT = treatment group
** CHG = Change of log-eGFR baseline ratio at 24 weeks
** BASE = log-baseline eGFR
*****

proc robustreg data=chg method=m (wf=huber) outest=chg1 covout;
  by _imputation_;
  class TRT;
  model CHG = BASE TRT;
run;
```

Pooling phase

In the pooling phase, the results from these 25 analyses will be combined using Rubin's method to construct the treatment estimate using the parameter estimates and associated standard errors. Sample SAS code below:

```
proc mianalyze data=chg1;
  modeleffects estimate;
  stderr stderr;
  ods output ParameterEstimates=est2;
run;
```

If the multiple imputation approach is such that the model convergence is questionable and the given parameter estimates cannot be obtained, then the ratio of eGFR at 24 weeks compared to baseline will be evaluated using similar MMRM model as for UPCR, otherwise, MMRM analysis will be considered as sensitivity analysis.

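### The efficacy models omit age group, the only stratification factor, which can make the 95% intervals wider than needed, and no safety or concentration summary shows adolescents separately

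*SAP*

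**What the plan says.** SAP 2.2.1 gives the design: "To ensure balance among treatment groups, randomization will be stratified by age group". Protocol 5.4 says the same and names no other factor. Age group also fixes two other things:

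- **Dose.** Protocol 5.1.1: "Patients will receive the following setanaxib doses according to age at the time of consent/assent". Adolescents take 800 mg in the morning and 400 mg in the evening; adults take 800 mg twice daily.
- **eGFR equation.** Protocol 7.3 uses CKD-EPI for adults "and the revised bedside Schwartz formula for patients 12 to 17 years of age".

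The models do not use it:

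- **UPCR (SAP 3.5.1).** "The model will include fixed effects for treatment, visit, and treatment by visit interaction, along with the log-transformed baseline value as a covariate". The sample PROC MIXED code agrees, and Protocol 9.2.2 lists the same terms.
- **eGFR (SAP 3.5.2).** "Robust Regression with independent variables of treatment and log-transformed baseline eGFR". The fallback or sensitivity MMRM is modelled on the UPCR one, so it has no age term either.

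Age category appears in the SAP analyses only as a baseline characteristic (SAP 3.3.4). No reason is given for leaving it out of the models.

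On adolescents, Protocol 1.5 says the results will be used "to assess the safety of setanaxib in this patient population, including adolescents", and Protocol 1.6.2 notes that the drug has not been tested in this age group. The SAE and AESI tables are by treatment group, system organ class and preferred term (SAP 3.4.1). Concentrations are summarised by treatment, nominal time and analyte (SAP 3.7.3), and SAP 2.2.1 puts both regimens in one setanaxib group.

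**The concern.** Stratifying makes the arms alike in age mix. If age group also predicts the outcome, that balance reduces the chance variation in the treatment estimate. A model without the factor takes no credit for this: the between-stratum difference stays in the residual, the standard error is overestimated, and the interval is wider than the design warrants. With about 18 patients, spare width is worth recovering.

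Separately, this is the first exposure of adolescents to the drug. With every summary pooled over age, the report would have no table showing how many adolescents had an event or what concentrations they reached. The pre-dose samples are a specific problem. They are taken before the morning dose, so they follow a 400 mg evening dose in adolescents and an 800 mg evening dose in adults. A pooled trough mean combines the two.

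**Working it through.** **The plan's own figures.** There is no power calculation to reproduce: Protocol 9.2.3 says the size was chosen empirically. The arithmetic is consistent: 18 at 2:1 is 12 and 6, and 6 adolescents + 12 adults = 18. Six adolescents is a cap. EU sites enrol adults only (Protocol 3.1), and the sites are in the UK and at least 2 other European countries (Protocol synopsis), so the adolescent stratum can hold anything from 0 to 6.

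**Cost of the term.** In a Week 24 analysis of covariance with 18 patients, treatment + baseline leaves 18 − 3 = 15 df, and adding age leaves 14. The ratio t(14)/t(15) is 2.1448/2.1314 = 1.006, so the loss of one df alone adds about 0.6% to the width.

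**Gain from the term.** Let d be the difference between age strata in mean log change, in residual SDs after baseline adjustment. The documents give no value, so d is an assumption, shown from 0 to 2. With one third adolescents, age contributes variance (1/3)(2/3)d² = 0.222d². Large-sample approximation to width without age divided by width with age:

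√(1 + 0.222d²) × 2.1314/2.1448

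- d = 0.5: √1.056 × 0.994 = 1.021
- d = 1: √1.222 × 0.994 = 1.099

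**Simulation.** 20,000 trials per case, n = 18, complete Week 24 data, normal residuals with SD 1, no treatment effect, baseline slope −0.3, and strata allocated at or near 2:1. Entries are mean 95% interval width without age divided by width with age, with coverage of the interval without age in brackets.

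| Adolescents (setanaxib:placebo) | d = 0 | d = 0.5 | d = 1 | d = 2 |
|---|---|---|---|---|
| 6 (4:2) | 0.993 (95.0%) | 1.023 (95.6%) | 1.111 (96.8%) | 1.409 (99.1%) |
| 3 (2:1) | 0.992 (95.0%) | 1.011 (95.4%) | 1.069 (96.3%) | 1.268 (98.3%) |
| 1 (1:0) | 0.978 (94.9%) | 0.984 (95.3%) | 1.006 (95.4%) | 1.084 (95.7%) |

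With 6 adolescents the simulation is close to the approximation (1.023 v 1.021, 1.111 v 1.099). At d = 0 the age term widens the interval by 1/0.993 − 1 = 0.7% with 6 adolescents and 1/0.978 − 1 = 2.2% with one. Break-even is at d of about 0.25 with 6 adolescents, between 0.25 and 0.5 with 3, and between 0.75 and 1 with one.

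The spread of the treatment estimate itself hardly changes (SD 0.523 without age and 0.519 with it, at d = 1 and 6 adolescents). What is lost lies in the estimated standard error, which is why coverage rises above 95%.

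**eGFR equations (Protocol Appendix B).** With creatinine above the equation's threshold and height constant, a 10% rise in creatinine gives an eGFR ratio of 1/1.1 = 0.909 by Schwartz and 1.1^(−1.209) = 0.891 by CKD-EPI. A constant offset between equations cancels in a within-patient ratio. This difference in scaling does not, and a main effect for age does not remove it.

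**Limit of the check.** It approximates the Week 24 contrast. It does not reproduce the full MMRM, the Huber regression or the multiple imputation.

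**The case against.** The strongest case for the plan is that the benefit is unproven. The documents give no age effect on either outcome, the adolescent stratum may be tiny or empty, and with one adolescent the term widens the interval unless d is close to 1. The analyses are secondary, no formal test is planned, and Protocol 9.2 calls all comparisons nominal. For UPCR the SAP follows the protocol's own model. All of this stands. It makes the gain conditional and calls for a minimum stratum size, but it does not explain leaving out the one factor the design balances.

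A reader might infer that the planned intervals are invalid or too narrow. They are not: every simulated coverage is 95% or above, within simulation error. A reader might also infer that adjusting for age deals with the two doses and the two eGFR equations. It does not. Different doses could produce a treatment-by-age difference, which a main effect does not model, and Protocol 5.3 says "the dose selection for adolescent patients aims to achieve the same systemic exposure levels as those seen in adults". The equations differ in scaling, as shown above.

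On the tables, Protocol Table 1 has no adolescent objective, percentages in at most 6 patients say little, and SAEs and concentrations are listed by patient (SAP 3.4.2 and 3.7.3). That is a fair reason to ask for counts and descriptive summaries only. Nor can it be said that the PK parameters lack an age split: SAP 3.7.4 leaves them to a separate analysis plan that is not among the documents.

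**Conclusion.** The point holds in a limited form. The UPCR MMRM, the eGFR robust regression and its fallback or sensitivity MMRM omit the only stratification factor without a stated reason. If age group predicts change after baseline adjustment, the intervals are conservative. With the full 6 adolescents the excess width is about 2% at d = 0.5 and 11% at d = 1, and it shrinks with fewer adolescents. If age group predicts nothing, the planned model is slightly the better one. The sizes rest on assumed values of d, complete data and strata close to 2:1.

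The request for age-group displays does not depend on d. It rests on the protocol's stated use of the results and, for concentrations, on pooling samples that follow different evening doses.

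**What to change.** - **Models.** Add age group as randomised as a fixed effect in PROC MIXED (UPCR, and the eGFR fallback or sensitivity MMRM) and in PROC ROBUSTREG, provided a pre-specified minimum is met. An example is at least 2 adolescents with data in the model, at least one of them in each arm. Otherwise use the current model. Dropping the term only when a stratum is empty would not be enough. In the Week 24 model a single adolescent is fitted exactly by the age term, and adolescents all in one arm give no within-stratum comparison. The per-arm condition can be checked only after unblinding, so it must be written as a fixed rule.
- **Imputation.** Leave it unchanged. Steps (a) and (c) in SAP 3.5.2 run separately by treatment, with 8 variables and about 6 placebo patients. An age term there would cost far more than one df and would be constant in the placebo arm if no adolescent received placebo.
- **Displays.** Show SAE and AESI counts and plasma concentrations by age group, descriptively. State in the SAP whether the separate pharmacokinetic plan splits its parameters by age.
- **Wording.** Say that the age term does not address treatment-by-age differences or the two eGFR equations, and that comparisons remain nominal.

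The cost is SAP wording, one model term (one df) and a few repeated tables, all before database lock. If the sponsor prefers to leave age out, one sentence giving the reason would do for the models.
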